# 1. INTRODUCTION

## 1.1 Disease

## Background

The keratocystic odontogenic tumor (KCOT) is a benign odontogenic neoplasm that has destructive and infiltrative behavior [1]. KCOT can occur as part of nevoid basal cell carcinoma syndrome (NBCCS) or as a sporadic case. KCOTs are the most prominent feature of NBCCS and they are present in 65-100% of cases [2]. Four to five percent of KCOT patients have NBCCS [3]. Although KCOTs are benign, they tend to be aggressive, with local invasion of bony structures, extensive growth, and potential for substantial disfigurement [4]. This condition has a high recurrence rate and it is estimated that after initial treatment with various procedures recurrence ranges from 2.5% to 62.5% [5]; [6]. The only therapeutic option for patients affected by KCOT is surgery which can involve significant destruction of tissue; often multiple surgeries are required. Thus, the management of patients with KCOT has challenged and frustrated both patients and providers [6].

Research findings suggest that mutations in *PTCH1* are frequent in both sporadic KCOT (29%) and NBCCS-associated KCOT (approximately 88%). Thus *PTCH1* gene mutations may play a significant role in the pathogenesis of NBCCS and the related sporadic tumors [7]. In this study, we plan to test GDC-0449 (Vismodegib) as novel treatment in two groups of patients: NBCCS-associated KCOT and sporadic KCOT cohort. The inclusion of this two-group cohort is based on the evidence that mutations of the hedgehog (Hh) pathway are present in both groups and consequently all patients affected by KCOT may benefit from a systemic Hh pathway antagonist.

We hypothesize that an inhibitor of the sonic Hh can be an important therapeutic advancement in the treatment of KCOT. This study proposes to test GDC-0449 (Vismodegib) for treating patients with KCOT. This drug has the potential to reverse KCOT proliferation. GDC-0449 may be useful as a neo-adjuvant prior to surgery in patients with KCOT or may be a surgery substitute in some cases. The use of GDC-0449 prior to surgery may lead to tumor shrinkage and reduce the extent of required surgery or eliminate the need for surgery completely.

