## **2. STUDY OBJECTIVES**

### **2.1 Primary Objectives**

The primary objectives of the study are:

- a. To evaluate the efficacy of GDC-0449 in reducing KCOT size (shrinkage) in NBCCS-associated KCOT and sporadic KCOT patients following 6 to 12 months of ingestion of 150 mg/day, up to 1 year of treatment and up to 2 years of post-treatment follow-up.
- b. To evaluate the safety of this dose of GDC-0449 in these patients.

*Tumor response (reduction in tumor volume and shrinkage) will be measured by volumetric CT scan.*

*Time Frame: Efficacy will be assessed at 1 year and 2 years after the study medication is stopped. Patients will undergo evaluation for 3 years (up to 1 year of treatment and up to 2 years of post-treatment follow-up). All patients will participate in the assessment of the safety and tolerability of the study drug. Safety monitoring will capture risks related to study participation and adverse events related to the study drug.*

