## 3. STUDY DESIGN

### 3.1 Description of the Study

This is a single-center, interventional, single-arm, open-label, two-cohort clinical trial. A total of 40 patients will be screened in order for 20 patients to be enrolled (10 with NBCCS-associated KCOT and 10 with sporadic KCOT) over a period of 2 years. This is a 3 year study where each patient will undergo up to 1 year of treatment and up to 2 years of post-treatment follow-up. If a patient is experiencing an ongoing adverse event at the time of the study completion, he/she will be followed-up until resolution of the adverse event or until the condition has stabilized. The same applies to patients who are withdrawn from the study due to adverse events.

It is estimated that it will take approximately 2 years to recruit 20 patients for the study (10 with NBCCS-associated KCOT and 10 with sporadic KCOT).

All patients will be assessed for safety and efficacy of the study drug GDC-0449 (Vismodegib).

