### **b. Efficacy Analysis**

#### **i. Primary Endpoint**

The effect of GDC-0449 will be evaluated (at a significance level of 5% and controlling the false discovery rate) using Wilcoxon signed rank tests to compare the mean KCOT volume at baseline to those acquired at 6, 12, 24,36 and 48 months. These comparisons will also be accomplished using paired t-tests.

ii. Subject population for this analysis. As a primary intention to treat (ITT) analysis, we will analyze data from all randomized subjects who complete Phase 1. For these analyses, Phase 1 values will be substituted for missing observations. Should more than 20% of the data be missing at any observation interval, analysis of that interval will be abandoned. Deviations from this plan, for example, emergent interest in the analysis of the all-treated or protocol-compliant subjects, will be transparently pursued and reported.

iii. Treatment of missing data. Two secondary effectiveness analyses will either carry the last observation forward into missing cells, or use maximum likelihood estimates of those values. We expect the best estimate of efficacy is likely to lie within the limits set by these conservative (ITT) and liberal (LOCF, ML) treatments of missing data.

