#### **iv. Secondary Endpoints**

Secondary analysis will quantify the proportion of patients achieving minimal clinically significant changes in their tumors and comparing that to a theoretical expectation of 5% improvement with a Fisher exact test, and the effect of the *PTCH1* mutation on tumor volume reduction will be assessed with an independent samples t-test. These analyses will use the same population as the primary endpoint.

All analyses will be done using IBM SPSS Version 21.

v. Sample size determination. Twenty subjects will be recruited. Analysis of the primary endpoint is capable of detecting changes in tumor volume in the Wilcoxon tests of approximately 1.0 and .68 SD, assuming a 2-tailed type 1 error of 5% and power of 80% and then assuming either n=10 (separate analysis of the NBCSS-associated and sporadic cohorts) or n=20 (combined analysis of both cohorts), respectively (G\*Power, v3.1).

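### The combined 20-patient test has no cohort term although the cohorts are fixed at 10 and 10, and a positive combined result would not by itself show an effect in sporadic KCOT

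*Combined protocol and SAP*

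**What the plan says.** The first primary objective (section 2.1) is "To evaluate the efficacy of GDC-0449 in reducing KCOT size (shrinkage) in NBCCS-associated KCOT and sporadic KCOT patients", so both patient types are named. Section 3.1 fixes the sample by cohort: "20 patients to be enrolled (10 with NBCCS-associated KCOT and 10 with sporadic KCOT".

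Section 4.8 b.i analyses tumour volume "using Wilcoxon signed rank tests to compare the mean KCOT volume at baseline to those acquired at 6, 12, 24,36 and 48 months" and adds that "These comparisons will also be accomplished using paired t-tests". Both are one-sample tests of the change from baseline. Neither carries a cohort term.

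Section 4.8 b.v gives the detectable change "in the Wilcoxon tests of approximately 1.0 and .68 SD", "assuming a 2-tailed type 1 error of 5% and power of 80" per cent, for "either n=10 (separate analysis of the NBCSS-associated and sporadic cohorts) or n=20 (combined analysis of both cohorts". Separate and combined analyses are therefore both planned. The section does not say which of them decides efficacy.

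Section 1.1 reports that PTCH1 mutations "are frequent in both sporadic KCOT (29%) and NBCCS-associated KCOT (approximately 88" per cent. It uses these rates to argue that both groups may benefit. Section 4.8 b.iv leaves the effect of PTCH1 on volume reduction to a secondary two-sample t-test.

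**The concern.** Cohort is known at entry and its size is set by design, but the combined test treats the 20 changes as one sample. Two consequences follow.

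- **Precision.** If the mean change differs between cohorts, the difference enters the SD that the combined paired t-test uses as its error. A model with a cohort term would remove it.
- **Interpretation.** A combined test asks whether there is a shift in a half-and-half mixture. It can be positive because of one cohort alone. Section 1.1 puts NBCCS at 4 to 5% of KCOT patients, so 95 to 96% are sporadic, while half the trial sample has NBCCS. A combined result therefore says least about the larger group, and the plan does not say on which analysis a statement about that group would rest.

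**Working it through.** **Inputs from the plan.** 10 patients per cohort (3.1); two-sided 5%, 80% power, detectable effects of 1.0 SD at n=10 and 0.68 SD at n=20 (4.8 b.v); mutation rates of 88% and 29% (1.1).

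**Assumptions.** Normal changes, within-cohort SD of 1, one time point, no missing values, no false-discovery adjustment. Adjustment and baseline substitution for missing values would lower all the powers below.

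**1. The plan's own figures.** A noncentral t with the normal-parent efficiency correction for the Wilcoxon test (effective n = n × 3/π) gives a detectable effect of 0.678 at n=20 (power at 0.68 is 80.3%) and 1.026 at n=10. Both agree with the stated approximate values.

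**2. What the pooled t-test uses as error.** With cohort means *m* + *h* and *m* − *h*, and 10 patients in each, the expected sample variance of the 20 changes is 1 + *h*² × 20/19. The cohort-adjusted test of the equally weighted mean uses the within-cohort variance, 1, on 18 degrees of freedom instead of 19.

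- Effects proportional to 88:29 with mean 0.68: the multiplier is 2 × 0.68 / (0.88 + 0.29) = 1.162, giving 1.02 and 0.34, so *h* = 0.34. Pooled SD = √(1 + 0.1156 × 20/19) = 1.059, and 0.68/1.059 = 0.642.
- Whole effect in NBCCS, 1.36 and 0: *h* = 0.68. Pooled SD = √(1 + 0.4624 × 20/19) = 1.219, and 0.68/1.219 = 0.558.
- Adjusted test in either case: noncentrality 0.68 × √20 = 3.04 on 18 df, power 82.0%.

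**3. Simulated power, 200,000 trials per row, exact signed-rank critical values.**

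| NBCCS / sporadic effect (SD) | Combined signed-rank | Combined paired t | Cohort-adjusted t |
|---|---|---|---|
| 0.68 / 0.68 | 80% | 82% | 82% |
| 1.02 / 0.34 | 76.5% | 79% | 82% |
| 1.36 / 0 | 65% | 68% | 82% |
| 0 / 0 | 5% | 5% | 5% |

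If the stated SD is instead the total SD of all 20 changes, the within-cohort SD in the 88:29 case is 0.936. The signed-rank test then has 81.6%, the paired t 83.8% and the adjusted t 86.7%. The signed-rank test loses nothing against its planned 80%, and the adjusted t still gains about 3 points over the pooled t.

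**4. Positive combined test with no sporadic effect.**

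| NBCCS effect (SD) | Combined signed-rank positive | Positive while the sporadic cohort's own test is not | Cohort-adjusted t positive |
|---|---|---|---|
| 1.0 | 44% | 42% | 56% |
| 1.36 | 65% | 62% | 82% |
| 2.0 | 88% | 85–86% | 99% |

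The sporadic cohort's own signed-rank test rejects in 5% of trials in every row, as it should. At 0.34 SD it has about 15% power, so a non-significant sporadic result is not evidence of no effect. The estimate and its interval are needed.

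**The case against.** The best defence is that the plan already separates the cohorts. Section 4.8 b.v provides an analysis of each at n=10, with its own detectable effect. That stands. A reader might infer that the plan as a whole ignores the two cohorts, and the documents do not support this: the missing term is in the combined analysis only. No section says that the combined test supports a claim for sporadic KCOT.

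A reader might also infer that unequal effects are the protocol's own expectation. They are not. The 88% and 29% are mutation rates, not effect sizes, and section 1.1 states no expected difference in response. The 88:29 split is my assumption, and 1.36/0 is an extreme.

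Nor should a large power loss be blamed on the missing term. With 0.68 SD in NBCCS and 0.22 SD in sporadic KCOT, combined signed-rank power falls to 44%. That is a smaller average effect: the paired t has 46% and the adjusted t only 48%.

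Adjustment does not protect the sporadic inference either. With no sporadic effect the adjusted test is positive more often than the pooled ones (82% against 65% and 68% at 1.36/0). Only the cohort-specific results and a stated rule for the claim do that.

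The power gain is also parametric: ranking within cohort lowers signed-rank power to 69% at 1.02/0.34. This is a reason to keep the planned signed-rank test alongside the model.

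Finally, running the comparisons in three overlapping populations with two tests each might suggest a definite inflation of false claims. Section 4.8 b.i promises false-discovery control without defining the family, so no size can be fixed from the documents.

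**Conclusion.** The point holds in a limited form. The combined analysis omits a known 10/10 design stratum. Including it costs essentially nothing when effects are equal (82% either way). It gains about 3 points over the pooled paired t-test under the 88:29 assumption and about 14 points in the extreme where sporadic KCOT does not respond. These figures rest on normal changes, equal within-cohort SDs and an average effect of 0.68 SD.

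The interpretive point needs only that the cohorts may differ: a positive combined test, pooled or adjusted, does not establish an effect in sporadic KCOT. Since the objective names both patient types, the plan should say where a claim for each would rest. This is an improvement worth making before analysis, not a flaw that invalidates the design.

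**What to change.** In section 4.8 b, for the combined analysis:

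- Fit the change in volume (or the log ratio to baseline) with cohort as a factor, and test the equally weighted mean of the two cohorts using the within-cohort variance on 18 degrees of freedom. Keep the planned signed-rank test alongside it.
- Report each cohort's estimate with a 95% confidence interval, and the between-cohort difference with its interval.
- State that any claim for sporadic KCOT rests on the sporadic cohort's own planned analysis, and that a positive combined test describes the mixture of the two cohorts.

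The cost is plan wording, one model term and one error degree of freedom (18 instead of 19), with no added patients, visits or scans. The real price is that the conclusion for sporadic KCOT will be less favourable if only the combined test is positive.

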#### c. Safety Analysis

All safety-related interventions, events, and findings will be summarized by incidence and duration and event classification. An adverse event will be considered treatment emergent if the onset date and time occur on or after the recorded clock time of the administration of study drug. Adverse events will be coded to preferred terms and system organ classes according to the Medical Dictionary for Regulatory Activities (MedDRA®). The severity of each adverse event will be determined from the World Health Organization (WHO) Toxicity Criteria or by protocol specified criteria. In addition, all adverse events will be assessed as to whether the onset of the event was related to the study drug or not and they will be followed to final resolution. Other safety assessments include vital signs, oral cavity examinations, and complete blood count. In the unlikely event that treatment is associated with increasing tumor size, tumor area, determined from panoramic radiographs acquired at each visit, will be compared to baseline.

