### Phase II BCNS Study (SHH4685s)

The anti-BCC efficacy of vismodegib was tested in a randomized, double-blinded, placebo-controlled, Investigator-sponsored trial in Gorlin syndrome (BCNS) patients with surgically eligible BCCs [13-15]. Forty-one patients were randomized 2:1 to receive oral vismodegib (n=26) or placebo (n=15). After a mean follow up of 8 months (range, 1 to 15 months), the per-patient rate of new surgically eligible BCCs (SEBs) was lower with vismodegib than with placebo (2 vs. 29 cases per group per year, p<0.001), as was the size (percent change from baseline in the sum of the longest diameter) of existing clinically significant BCCs (–65% vs. –11%, p=0.003). In some patients, all BCCs clinically regressed. No tumors progressed during treatment with vismodegib. Patients receiving vismodegib routinely had Grade 1 or 2 AEs of loss of taste, muscle cramps, hair loss, and weight loss. Overall, 54% of patients (14 of 26) receiving vismodegib discontinued drug treatment due to AEs. At 1 month, vismodegib use had reduced the Hh pathway's target-gene expression in BCC cells by 90% (p<0.001) and diminished tumor-cell proliferation, but apoptosis was not affected. No residual BCC was detectable in 83% of biopsy samples taken from sites of clinically regressed BCCs. At the second pre-specified interim analysis, a data safety and monitoring board concluded that the pre-determined threshold for a significant difference between the two groups had been reached (p<0.0113), and the treatment with placebo in this arm was terminated. AEs reported in ≥10% of patients are summarized in Table 9 See the Vismodegib Investigator's Brochure and the U.S. package insert for additional details on nonclinical and clinical studies on vismodegib.

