### **Adverse Event Reporting Period**

The study period during which all AEs and SAEs must be reported begins after informed consent is obtained and initiation of study treatment and ends 30 days following the last administration of study treatment or study discontinuation/termination, whichever is earlier. After this period, investigators should only report SAEs that are attributed to prior study treatment. All AEs occurring from the start of study treatment through to study completion, whether or not they are related to the study, will be recorded in the subject chart.

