APPENDIX A: SCHEDULE OF STUDY ASSESSMENTS & PROCEDURES

STUDY ASSESSMENTS & PROCEDURES	SCREENING PHASE	TREATMENT PHASE (1 YEAR)											POST TREATMENT FOLLOW UP (2 YEARS)							
	BASELINE VISIT	1 MONTH POST DOSING	2 MONTH POST DOSING	3 MONTH POST DOSING	4 MONTH POST DOSING	5 MONTH POST DOSING	6 MONTH POST DOSING	7 MONTH POST DOSING	8 MONTH POST DOSING	9 MONTH POST DOSING	10 MONTH POST DOSING	11 MONTH POST DOSING	1 YEAR POST DOSING	1 MONTH POST TREATMENT	2 MONTH POST TREATMENT	3 MONTH POST TREATMENT	7 MONTH POST TREATMENT	1 YEAR POST TREATMENT	2 YEARS POST TREATMENT	DISCONTINUATION VISIT
		+/- 7 DAYS																		
Informed Consent & Screening	X																			
Review of Inclusion/Exclusion Criteria	X																			
Review of Medical Records, if applicable	X	X	X	X	X	X	X	X	X	X	X	X	X	X	X	X	X	X	X	X
Medical/Dental History	X	X	X	X	X	X	X	X	X	X	X	X	X	X	X	X	X	X	X	X
Concomitant Medications	X	X	X	X	X	X	X	X	X	X	X	X	X	X	X	X	X	X	X	X
Demographics (height, weight)	X																			
Urine Pregnancy Test, if female patient of child bearing potential		X	X	X	X	X	X	X	X	X	X	X	X	X	X	X	X	X	X	X
Serum pregnancy test, if female patient of child bearing potential	X	*	*	*	*	*	*	*	*	*	*	*	*	*	*	*	*	*	*	*
Oral Cavity Assessment (soft & hard tissues)	X	X		X			X									X	X	X	X	
Physical Exam	X	X		X			X						X							X
Clinical Laboratories	X			X			X						X							X
Genetic Testing of Blood	X												X							X
Genetic Testing of the Tumor, if biopsy on excision	X												X							X
Vital Signs (BP, HR, temperature)	X	X		X			X						X				X	X	X	X
Verification of KCOT Diagnosis	X																			
Biopsy of Tumor, if applicable	X																			
Panoramic Radiograph	X	X		X			X						X				X	X	X	X
Volumetric CT Scan	X						X						X					X	X	X
Skin Examination for NBCCS-associated KCOT patients	X						X						X					X		X
Photographs of Skin Lesions, if applicable	X						X						X					X		X
Study Drug Administration – First Dose	X																			
Study Drug Dispense until next visit / Compliance with study drug	X	X	X	X	X	X	X	X	X	X	X	X	X							
Continuance Criteria/Study Reminders		X	X	X	X	X	X	X	X	X	X	X	X	X	X	X	X	X	X	
Adverse Events	X	X	X	X	X	X	X	X	X	X	X	X	X	X	X	X	X	X	X	X
Study completion, Discharge																				X

\* Any positive urine pregnancy test must be confirmed by a serum pregnancy test.

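### The treatment-emergent rule in Section 4.8.c has no closing date, so up to two off-drug years count as treatment-emergent; the end of the reporting period in Section 5.2 is also ambiguous

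*Combined protocol and SAP*

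**What the plan says.** Two windows are involved: one for analysis and one for reporting.

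**Analysis window (Section 4.8.c).** "An adverse event will be considered treatment emergent if the onset date and time occur on or after the recorded clock time" of study drug administration. No closing date follows, and no separate table of post-treatment events is planned.

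**How long AEs are collected.** Section 3.1 says that "each patient will undergo up to 1 year of treatment and up to 2 years of post-treatment follow-up". Section 4.4.4 lists adverse events among the procedures at 1, 2, 3 and 7 months and at 1 and 2 years after treatment. The Adverse Events row of Appendix A marks the same visits and the discontinuation visit. Section 5.2 adds that "All AEs occurring from the start of study treatment through to study completion, whether or not they are related to the study", go into the subject chart.

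**Reporting window (Section 5.2).** It opens once the patient has consented and has started the drug. The closing clause says that it "ends 30 days following the last administration of study treatment or study discontinuation/termination, whichever is earlier". After that, only serious adverse events (SAEs) attributed to prior study treatment are reportable.

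**The concern.** Safety is one of the two primary objectives (Section 2.1) and there is no control arm, so the treatment-emergent table is the main safety result and no comparator rate corrects it. A rule that opens at dosing and never closes puts an event in month 35 in the same column as one in week 3.

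Two kinds of late event would enter: ordinary intercurrent illness, and disease returning after the drug is stopped. Section 5.1 counts new signs or symptoms of the tumour as AEs, and Section 4.4 (Dermatologic Assessments) records baseline signs that worsen during or after dosing. The relatedness assessment does not remove either kind from the count, because the definition depends on onset time alone.

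The window length also varies with outcome. A patient who completes contributes about three years. One released for toxicity under the continuance criteria may contribute much less.

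The reporting clause raises a separate question: whether a patient who leaves early still has all AEs reported for 30 days after the last dose.

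**Working it through.** **1. The plan's own figure.** Up to 12 months on drug plus up to 24 months of follow-up is 36 months, which matches the 3-year study length in Section 3.1.

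**2. Share of the open window that is off drug, for a patient who completes.**
- Off drug: 24/36 = 67%.
- A window closed at last dose + 30 days lasts 365.25 + 30 = 395.25 days. The open window lasts 3 × 365.25 = 1,095.75 days.
- Beyond last dose + 30 days: (1,095.75 − 395.25)/1,095.75 = 700.5/1,095.75 = 64%, or about 23 of 36 months.

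**3. Effect on incidence.** The documents give no background rate, so this step is illustrative. Assume an unrelated event with constant rate λ per patient-year, and all 20 patients observed for 3 years. Then P(at least one event) = 1 − exp(−λT), with T = 3 years (open) or 395.25/365.25 = 1.082 years (closed).

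| Assumed λ | Closed window | Open window | Expected patients of 20 (closed / open) | Ratio |
|---|---|---|---|---|
| 0.02 | 2.1% | 5.8% | 0.4 / 1.2 | 2.7 |
| 0.05 | 5.3% | 13.9% | 1.1 / 2.8 | 2.6 |
| 0.1 | 10.3% | 25.9% | 2.1 / 5.2 | 2.5 |
| 0.2 | 19.5% | 45.1% | 3.9 / 9.0 | 2.3 |
| 0.5 | 41.8% | 77.7% | 8.4 / 15.5 | 1.9 |

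For λ = 0.1: 1 − exp(−0.1 × 1.082) = 0.103 and 1 − exp(−0.1 × 3) = 0.259; 0.259/0.103 = 2.5.

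These ratios do not apply to the drug's familiar effects. The expanded access study in Section 1.3.1.1 gives median onset times of 30 to 175 days, so most such events would fall in either window.

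**4. Readings of the closing clause in Section 5.2.**
- *A.* The 30 days apply to both anchors. Since the last dose normally comes on or before exit, the period ends 30 days after the last dose.
- *B.* The period ends at the earlier of last dose + 30 days and the date the subject leaves the study.
- *C.* The discontinuation meant is closure of the trial, as in the heading of Section 4.7. Patient exit is Section 4.6, under a different heading. A subject's own exit then has no effect.

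Only B shortens the period for a patient who leaves. The loss is 30 days minus the gap between last dose and exit, and not less than zero:
- no gap: 30 days
- 14 days: 16 days
- one month or more: none, because last dose + 30 days has passed or is about to pass. After three months it passed about 61 days before exit.

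**5. What reading B would miss.** Attributed SAEs stay reportable (Sections 5.2 and 5.3.f). Ongoing events are followed to resolution or stabilisation, including in patients withdrawn for AEs (Section 3.1). The discontinuation visit records AEs (Section 4.6, Appendix A). What remains is new non-serious AEs and unattributed SAEs arising between that visit and day 30. Section 5.3.b ties the reporting of deaths regardless of attribution to this same period.

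**The case against.** The strongest defence of the analysis rule is that Section 5.1 describes AEs as events emerging in the protocol-specified reporting period, which Section 5.2 closes no later than 30 days after the last dose. On that view later events are charted but need not be tabulated as treatment-emergent. Onset dates and relatedness are recorded, so an analyst could separate on-drug from off-drug events, and the safety summaries are descriptive, with no test to bias.

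Part of this stands: the data will allow the separation. But the list in Section 5.1 is inclusive and does not limit Section 4.8.c, and Section 5.2 itself calls later events AEs and keeps collecting them. The plan therefore supports two different counts and does not say which will be published. A descriptive incidence is still misleading if its window is mostly off drug.

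On reporting, the objection is stronger. A reader might infer that mandatory reporting simply stops when a patient is discontinued for toxicity. The text does not establish that: it is one of three readings, and attributed SAEs and ongoing events remain covered on all of them. A reader might also multiply 20 patients by the AE discontinuation rates cited in Section 1.3.1.1, 35.6% in the large safety study and, in the Gorlin syndrome trial, "54% of patients (14 of 26) receiving vismodegib discontinued drug treatment due to AEs". Those are rates of stopping drug in other populations. This protocol treats stopping drug (Section 4.5) separately from leaving the study (Section 4.6), so the product does not count patients who would lose reporting.

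**Conclusion.** The concern about the treatment-emergent rule holds. As written, for a patient who completes follow-up, 24 of 36 months are off drug and 23 of 36 lie beyond last dose + 30 days. The resulting inflation of about 1.9 to 2.7 times for an unrelated event rests on assumed constant rates of 0.02 to 0.5 per patient-year and on all 20 patients completing 3 years. Early departures would reduce it, and at the lowest rate it is less than one extra patient (1.2 against 0.4 of 20).

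The reporting clause is a secondary matter of ambiguity. On one reading, new non-serious AEs and unattributed SAEs could go unreported for up to 30 days after the last dose in a patient who leaves. The documents do not allow the number affected to be estimated.

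A reader might infer that the windows are also wrong at their start. The documents do not support that: both open with study treatment, and both problems are at the closing end.

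**What to change.** **Section 4.8.c.** Define treatment-emergent as onset or worsening from the first dose through 30 days after the last dose, the interval already in Section 5.2. Tabulate later-onset events separately as post-treatment events. Nothing collected is discarded.

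**Section 5.2.** State that the all-AE reporting period runs to 30 days after the last dose, including for patients who leave the study early, unless consent is withdrawn or contact is lost. Remove the earlier-of-two-dates condition.

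**To reconcile.** Section 4.4 (Potential Risks to Participants) allows a toxicity break of one to three months, while Section 4.5 limits an interruption for intolerable toxicity to two consecutive weeks. The two affect how far exit lies from the last dose and must be reconciled; no rule is proposed here.

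**Cost.** Two short text changes, one extra table, and a day-30 contact for patients who leave early, by telephone or at the 1-month post-treatment visit if they still attend. A few more events may need reporting.
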